#### **Retinal detachment**

Patients that experience retinal detachment of grade 2 or higher according to CTCAE v4.03 have to be permanently discontinued from study treatment.

## 8.4.4 Dose-limiting toxicity (DLT)

Adverse events which qualify as DLTs are causally related to study drug (while in turn not all related AEs are regarded as DLT). Dose-limiting toxicity will be defined as any of the following occurring during Cycle 1 of a dose level and regarded by the investigators and / or sponsor to be related to BAY 1163877. The CTCAE v 4.03 will be used to assess toxicities / adverse events (see Section 16.5).

#### Hematological

- Absolute neutrophil count (ANC) < 500/mm^3 for more than 7 days
- Febrile neutropenia (a disorder characterized by an ANC  $< 1,000/\text{mm}^3$  and single temperature  $\ge 38.3$  °C or sustained temperature of  $\ge 38.0$  °C for more than 1 hour)
- Platelets  $< 25,000/\text{mm}^3$
- Grade 3 hemorrhage associated with thrombocytopenia of  $\geq$  Grade 3

17 Oct 2018 Version 8.0 Page: 65 of 395

#### Non-hematological

- Non-hematologic Grade 3 or Grade 4 toxicity (nausea and vomiting only if refractory to anti-emetics; excluding alopecia). A maximum duration of 48 hours of Grade 3 nausea or vomiting will be allowed and not be considered DLT.
- Serum calcium (albumin-corrected) x phosphate product  $> 70 \text{ mg}^2/\text{dL}^2$  (5.6 mmol/L) despite the use of phosphate binders

#### Miscellaneous

In case an unexpected drug-related toxicity is seen more frequently, this toxicity may be declared a DLT for the remainder of the study after thorough consultation between the investigator and the sponsor.

Any toxicity thought to be related to BAY 1163877 that, at the discretion of the investigator, or his designated associate(s), is thought to warrant withholding the drug. Such toxicities might be Grade-1 or Grade-2 toxicities which interfere with the activities of daily life (e.g. long-lasting fatigue, or anorexia), making a dose reduction necessary in order to ensure the subject's compliance.

For certain toxicities such as laboratory assessments without a clear clinical correlation (e.g. lipase increase without signs of a clinical pancreatitis), a discussion between the investigator and the sponsor may take place if that adverse event should be assessed as DLT necessitating dose reduction.

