- The possible maximum dose of BAY 1163877 is considered to be 550 mg b.i.d. (1100 mg / day). Higher doses might be explored after discussions between sponsor and investigators.
- If at least 1 subject out of 3 or 1 out of 4 in a cohort has DLTs or if at least 2 subjects report drug-related AEs (CTCAE v4.03) of Grade ≥ 2, any further dose escalation, de-escalation or cohort expansion will be decided in consultation between all investigator(s), and the sponsor (within the DSMT) after consideration of all available safety data of the previous cohorts. Any subsequent dose will be selected in order to determine the MTD.

17 Oct 2018 Version 8.0 Page: 42 of 395

Model-based dose-response analysis of the DLT rates will be performed during these interim reviews in order to guide the dose decision (see details in Section 16.4). The model-based dose selection procedure is considering data at all dose levels (not just at the last cohort). The dose predicted to yield 20% DLT rates will be reported from that model as a best candidate for the next cohort.

The final decision about the next dose will be made by the sponsor in consultation with all investigators (DSMT).

If the selected dose is larger than the last dose tested, then escalation will be pursued. If it is lower, a de-escalation step will occur.

Cohort expansion will occur when a previously tested dose is selected again for the next cohort of 3 subjects.

Expansions at any given dose up to a total of 9 subjects are allowed. In principle, the selection of a next dose level where the predicted DLT rate is close to 20% should insure that the next dose tested will remain safe.

[figure not shown]
Nevertheless, the following constraint will be added in order to protect subject safety during the adaptive dose selection decisions:

- If 2 out of 3 (or 2 out of 4), at least 4 out of 6 (or at least 5 out of 9) subjects experience DLTs at a given dose level, only lower doses will be given in all subsequent cohorts because the probability that the dose is above the MTD is very large (above 95.4%).
- The dose-escalation procedure will be stopped as soon as:
- the MTD has been defined with good precision (i.e., the coefficient of variation for the MTD is lower than or close to 40%)
- o at any time when the selected dose level for the next cohort has already been given in 9 subjects.

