#### 9.5.1.2.2 Intensity

The intensity / severity of an AE will be graded using the CTCAE v4.03, see Section 16.5. For events not listed in the CTCAE v4.03 the following scale will be used:

Grade 1 = Mild AE, transient in nature and generally not interfering with normal activities

No. BAY 1163877 / 16443

17 Oct 2018 Version 8.0 Page: 96 of 395

Grade 2 = Moderate AE, sufficiently discomforting to interfere with normal activities

Grade 3 = Severe AE, prevents normal activities

Grade 4 = Life-threatening and / or disabling AE

Grade 5 = Results in death (fatal)

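### A toxicity added to the DLT definition mid-study applies from then on, with no re-scoring of earlier cohorts, while one dose-DLT curve is fitted to all cohorts

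*Protocol*

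**What the plan says.** The primary variable is the incidence of DLTs in Cycle 1 (Protocol Section 6.1), and Section 8.4.4 defines a DLT. Under its Miscellaneous heading: "In case an unexpected drug-related toxicity is seen more frequently, this toxicity may be declared a DLT for the remainder of the study", after consultation between investigator and sponsor. The step is optional and its stated scope runs forward. Neither Section 8.4.4 nor Section 10.4.2 says what happens to Cycle 1 data already evaluated.

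Section 6 says of the model that guides dose selection: "The model-based dose selection procedure is considering data at all dose levels (not just at the last cohort". Section 10.4.2 then regresses Cycle 1 DLT on dose by Bayesian logistic regression and derives the MTD from the intercept and slope. The one sensitivity analysis named there varies the prior, not the DLT definition.

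On severity, the graded non-hematologic item reads "Non-hematologic Grade 3 or Grade 4 toxicity (nausea and vomiting only if refractory to anti-emetics; excluding alopecia". Section 9.5.1.2.2, in the scale for events not listed in CTCAE, has "Grade 5 = Results in death (fatal". Section 8.4.3 uses an open-ended Grade 3 and above when it deals with drug-related events.

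**The concern.** A logistic curve of DLT on dose can be interpreted only if a DLT means the same thing at each dose. Escalation starts at 100 mg/day and normally moves up, so a definition adopted part-way is mostly a definition for the higher doses. A subject at a low dose who had the toxicity before it was declared stays DLT-free; a later subject with the same event counts. The model has no term for the change and reads it as a dose effect. The slope becomes too steep, the low doses look cleaner than they were, and the dose predicted to give a 20% DLT rate moves up relative to consistent scoring. That dose is both the candidate for the next cohort and the primary outcome.

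The Grade 5 wording is a different kind of problem. The most serious outcome is not named in the graded item that a reader would consult first.

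**Working it through.** **Text check.** Section 8.4.4 makes the added DLT apply forward. Sections 6 and 10.4.2 use all cohorts on one curve. Read together, and if the clause is used as written, early subjects enter the fit on the narrow definition and later subjects on the wide one.

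**No plan figure to reproduce.** Section 8.4.4 gives no number that depends on this clause. What follows only illustrates direction and size.

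**Illustration A: logistic fit to expected counts, no prior.** The prior is in Section 16.4, which was not in the text available.
- Taken from the protocol: target rate 20%; MTD = (log(0.2/0.8) − intercept)/slope (Section 10.4.2).
- Assumed: doses 100/200/400/600/800 mg/day with n = 3/3/3/6/9.
- Assumed narrow-definition DLT rate: 3% at 100 and 20% at 800. The slope is (log 0.25 − log(0.03/0.97))/700 = 0.002985 and the intercept −3.775, giving rates of 3.0, 4.0, 7.0, 12.1 and 20.0% and a narrow-definition MTD of 800.
- Assumed added toxicity, independent of the other DLTs: rate q at 800, either proportional to dose or the same at all doses. Wide rate = 1 − (1 − narrow)(1 − added).
- Mixed scoring uses the wide rate only from 600, or only from 800, upward.

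Example, q = 10% at all doses, wide from 600:
- Consistent rates 12.7, 13.6, 16.3, 20.9, 28.0% give intercept −2.163 and slope 0.001485, so MTD = (−1.386 + 2.163)/0.001485 ≈ 523.
- Mixed rates 3.0, 4.0, 7.0, 20.9, 28.0% give intercept −3.715 and slope 0.003555, so MTD = (−1.386 + 3.715)/0.003555 ≈ 655.
- The gap is 655 − 523 = 132 mg/day.

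| Added toxicity | q | Consistent MTD | Mixed, from 600 | Mixed, from 800 | Gap |
|---|---|---|---|---|---|
| Proportional to dose | 5% | 717 | 723 | 741 | 6–24 |
| Proportional to dose | 10% | 642 | 667 | 701 | 25–59 |
| Proportional to dose | 15% | 576 | 624 | 672 | 48–96 |
| Same at all doses | 5% | 693 | 717 | 741 | 24–48 |
| Same at all doses | 10% | 523 | 655 | 701 | 132–178 |
| Same at all doses | 15% | 298 | 607 | 672 | 309–374 |

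All 12 comparisons give a steeper slope and a higher MTD under mixed scoring.

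**Illustration B: simulated trials with a weak prior.** Assumed: six cohorts from 100 to 1100 mg/day, n = 3, 3, 3, 3, 3, 9; base DLT rates 1, 2, 4, 6, 9, 14%; added toxicity declared from the fourth cohort.
- Added rate 12% at every dose: the first nine subjects carry 9 × 0.12 ≈ 1.1 uncounted events. Median MTD 856 re-scored against 1035 mixed (1035/856 = 1.21, +21%). Other weak-prior fits of the same setup gave 874 against 1029 (log-dose, +18%) and 924 against 1023 (linear dose, +11%).
- Added rate proportional to dose (12% at 1100 or at 800): +1% to +5%, about 11 to 56 mg/day.
- Added toxicity appearing late (0, 0, 3%, then 12%): no change in the median.

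**Grade 5.** Side by side, Section 8.4.4 closes the range at Grade 4, Section 9.5.1.2.2 has a separate fatal Grade 5, and Section 8.4.3 leaves its range open upward. The three do not settle how a related fatal event is classified for the endpoint.

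**The case against.** The strongest reply is that this is conditional and partly guarded against. The clause says the toxicity may be declared, and nothing forbids re-scoring. The model only guides: the sponsor with the investigators decides the next dose, and two subjects with drug-related events of Grade 2 or higher already trigger a review of all earlier safety data, whatever their DLT label. Section 8.4.4 counts, from the first cohort, related toxicities that the investigator thinks warrant withholding the drug ("Such toxicities might be Grade-1 or Grade-2 toxicities which interfere with the activities of daily life"), so the clause adds mainly events not judged to warrant that. De-escalation and re-expansion are allowed, so time and dose are not perfectly aligned. Section 16.4 and the SAP, neither available here, might state a coding rule. All of this narrows the problem. It does not remove it: the protocol states a forward scope in the section that defines its primary endpoint, and reviewing safety data does not recode what enters the regression.

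Four stronger readings are tempting but unsupported.
- That the DLT list holds only Grade 3–4 non-hematologic toxicity. It also has four hematologic items (for example "Febrile neutropenia (a disorder characterized by an ANC" below a stated count, with fever), a calcium-phosphate criterion ("despite the use of phosphate binders"), the discretionary lower-grade item, and laboratory events where "a discussion between the investigator and the sponsor may take place if that adverse event should be assessed as DLT".
- That the missing Grade 5 mixes endpoints across doses. That wording is the same at every dose.
- That the endpoint already differs between low and high doses. It would do so only if the clause is used, no one re-scores, and the toxicity had occurred earlier.
- That a related death would go uncounted. A subject who discontinued in Cycle 1 because of an adverse event is in the MTD evaluation (Section 10.2), and the discretionary clause could apply; the documents leave the classification implicit.

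**Conclusion.** The point holds as a conditional one. If Section 8.4.4 is used as written, the fit in Sections 6 and 10.4.2 combines subjects scored on a narrower and a wider endpoint, and the usual order of escalation tilts the estimated MTD upward. The direction was the same wherever a shift appeared. The size was not: none or a few mg/day for a late or strongly dose-related toxicity, up to 96 mg/day in the proportional cases, and about 100 mg/day or more for a toxicity of 10% or higher at all doses (+11% to +21% in the six-cohort setup, as much as 374 mg/day in the most extreme five-dose case). The +21% figure should not be read as the expected bias, because it assumes a toxicity unrelated to dose. All figures rest on assumed rates and fixed cohort sizes, and none uses the protocol's own prior. At Version 8.0 the expansion parts already build on the Part 1 MTD, so some dose decisions may lie in the past; the final MTD analysis can still be protected. The Grade 5 gap is a separate matter of wording, with no magnitude attached.

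**What to change.** In Sections 8.4.4 and 10.4.2, add: when a toxicity is newly declared a DLT, the Cycle 1 adverse-event data of all subjects already treated are re-scored on the revised definition before the next model run and before the final MTD analysis; results on the original definition are reported as a sensitivity analysis. If Section 16.4 or the SAP already holds such a rule, cite it in Section 8.4.4 and align the forward-looking wording with it.

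Separately, reconcile the graded non-hematologic item in Section 8.4.4 with Sections 8.4.3 and 9.5.1.2.2, so that the endpoint classification of related fatal events is explicit. The sponsor and investigators decide what that classification is.

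The cost is a few sentences and some re-coding of adverse events already graded and recorded in the eCRF; no new data are needed. The revised scoring may give a lower MTD estimate.

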#### 8.5 Blinding

The study is performed in a non-blinded design because this is considered adequate to meet the study objectives.

## 8.6 Drug logistics and accountability

Study medication will be stored at the investigational site in accordance with good clinical practice (GCP) and GMP requirements and the instructions given by the clinical supplies department of the sponsor (or its affiliate / contract research organization (CRO)), and will be inaccessible to unauthorized personnel. Special storage conditions and a complete record of batch numbers and expiry dates can be found in the Sponsor study file; the site-relevant elements, of this information will be available in the ISF. The responsible site personnel will confirm receipt of study drug in writing and will use the study drug only within the framework of this clinical study and in accordance with this protocol. Receipt, distribution, return and destruction (if any) of the study drug must be properly documented according to the sponsor's agreed and specified procedures.

Written instructions on medication destruction will be made available to affected parties as applicable.

17 Oct 2018 Version 8.0 Page: 66 of 395

## 8.7 Treatment compliance

#### **Treatment compliance**

The first administration of study medication (BAY 1163877) will be done with a member of the site team. This person will ascertain and document that the subject receives the treatment as planned.

On the following days the subject will self-administer (or a caregiver will administer) BAY 1163877 after he / she has been informed about the correct dosing schedule.

Plasma / serum concentrations will give additional information about the subjects' treatment compliance.

At home, subjects will document the intake of study drug (date and time of dosing) as well as the administered dose on a compliance sheet / paper diary (source document to verify treatment compliance), see Section 9.6.1.

The packages of study medication have to be brought back to the trial site for an additional control.

Compliance will be evaluated by the investigational site based on drug accountability.

The information recorded in the paper diary will be transferred into the eCRF taking into account each dose interruption and / or any individual changes in dosing.

A compliance of at least 80% is required, meaning documented intake of at least 80% of the planned study medication (80 % = 32 doses or 16 days in Cycle 1 with PK assessment [Part 1 and Part 2 only] and 34 doses or 17 days in  $\geq$  Cycles 2 and in Cycle 1 without PK assessment [including Part 3]). 

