When a subject starts new anti-cancer therapy, he / she is no longer considered "on study". An End of Treatment (EOT) visit will be performed for all subjects within 0-14 days after

<sup>32 Part 3 - Safety cohort - was added by Amendment 7, see section 15.6.2.6

17 Oct 2018 Version 8.0 Page: 40 of 395

administration of the last dose of BAY 1163877. The Follow-up visit for subjects who either discontinue prematurely or finish dosing with BAY 1163877 will be performed 30-35 days after the last study drug treatment. There will be no long-term (survival) follow-up (FU) period.

Treatment: Subjects with PK assessment (all subjects of study Part 1 and 3 and at least 12 subjects of study Part 2 and approximately 8 subjects of the MTD expansion cohorts with impaired renal function at baseline) will receive BAY 1163877 (tablet or solution) on a continuous schedule starting with single-dose administration on Cycle 1, Day 1, followed by a "drug-free day" (to enable single dose PK assessments, except for subjects in Part 3 who will receive BAY 1163877 twice daily continuously with no "drug free day"). Treatment with BAY 1163877 will resume on Day 3 of Cycle 1 if no protocoldefined dose-limiting toxicities (DLTs) are reported. Starting on Cycle 1, Day 3, the study drug will be self-administered twice daily for the remaining 19 days of Cycle 1. For subsequent cycles, study drug will be administered twice daily for 21 days until disease progression or as long as clinical benefit is assumed by the investigator or until unacceptable toxicity occurs.

In one of the dose escalation cohorts in study Part 1 ("tablet bridging cohort"), relative bioavailability of the tablet formulation will be assessed by administration of a single dose of the tablet formulation on Cycle 1, Day -3. Starting with Cycle 1, Day 1, subjects enrolled in the "tablet bridging cohort" will continue with the solution formulation as described above. Depending on the results from the relative bioavailability assessment, subjects who initially start with solution formulation may be switched to tablet formulation in later cycles.

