## 7.2.2 Replacement

Subjects who discontinue due to a DLT will NOT be replaced.

Subjects who discontinue during the first cycle of therapy (Cycle 1) due to any reason other than a DLT and / or related toxicity, and subjects who took less than 80% of the required study drug (BAY 1163877) in Cycle 1 (see Section 8.7) will be replaced to ensure 3 evaluable subjects per cohort for the determination of MTD and PK of BAY 1163877. Subjects who discontinue after the first cycle (Cycle 1) will not be

 Withdrawal criteria were added by Amendment 6, see section 15.6.2.12

17 Oct 2018 Version 8.0 Page: 55 of 395

replaced.

Subjects enrolled in Study Part 1 / MTD expansion (all comer) with insufficient paired biopsy samples will be replaced to ensure at least 10 subjects with paired biopsy samples for p-ERK1/2 analysis.

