## 8.4.2.1 Dosing schedule - amended

BAY 1163877 will be given in cycles. Each cycle lasts 21 days. There will be no break between treatment cycles.

Subjects will receive either the solution (IMP 1) or the tablet (IMP 2) formulation of BAY 1163877, except for subjects in the "tablet bridging cohort" who will receive both a single dose using the tablet formulation and multiple doses using the solution formulation.

Study Part 1 / dose escalation + MTD expansion cohort (all comer):

Cycle 1 Day -3 ("tablet bridging cohort" only): Single-dose administration of

BAY 1163877 tablet formulation on Cycle 1, Day -3; thereafter continuation with solution formulation starting on Cycle 1, Day 1 (see dosing schedule

below)

Cycle 1: Single-dose administration of BAY 1163877 on

Cycle 1, Day 1 (in the morning)

No administration of BAY 1163877 on Cycle 1,

Day 2 ("drug-free day")

Twice daily administration of BAY 1163877 on

Days 3-21

Cycle 2 and subsequent cycles: Twice daily administration of BAY 1163877 on

Days 1-21.

Study Part 2 / dose expansion (sqNSCLC + LAC + BC + SCCHN):

- Subjects participating in PK assessments will follow the dosing regimen specified for study Part 1.
- Subjects without PK assessment will receive BAY 1163877 twice daily from Cycle 1, Day 1 ongoing.

Study Part 1 (MTD expansion cohort) or Study Part 2 / "Food Effect Assessment": Approximately 8 subjects will receive single doses of BAY 1163877 on Cycle 1, Day -3 (after consumption of a high-fat, high-calorie breakfast) and on Cycle 1, Day 1 (after an overnight fast of at least 8 hours). BAY 1163877 will not be administered on Cycle 1, Day -2 and Day -1, in the evening of Cycle 1, Day 1 and on Cycle 1, Day 2.

[figure not shown]
Study Part 3 / MTD expansion "Safety cohort" (sqNSCLC + LAC + BC):

• Subjects will receive BAY 1163877 twice daily from Cycle 1, Day 1 ongoing.

-

<sup>48 Part 3 added by Amendment 7, see section 15.6.2.14

<sup>49 Part 3 - Safety cohort - was added by Amendment 7, see section 15.6.2.15

17 Oct 2018 Version 8.0 Page: 60 of 395

Evidence of tumor progression, unacceptable toxicity, consent withdrawal or subject's withdrawal from the study at the discretion of the Investigator may lead to termination of treatment (see Section 7.2.1).

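### Section 8.7 gives two limits for 80% compliance in Cycle 1 with PK assessment, 32 doses or 16 days, that differ by one dose if the single-dose Day 1 counts as a dosing day

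*Protocol*

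**What the plan says.** Section 8.7 (Treatment compliance) sets the rule as a share of drug: "A compliance of at least 80% is required, meaning documented intake of at least 80% of the planned study medication". A parenthesis then turns the share into counts. For subjects on the PK schedule it reads "80 % = 32 doses or 16 days in Cycle 1 with PK assessment". For later cycles, and for Cycle 1 without PK assessment, it gives 34 doses or 17 days.

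The schedule behind the first pair is in Section 8.4.2.1 (Dosing schedule) and in the treatment paragraph of Section 6. A single dose is given on the morning of Day 1, Day 2 is drug-free, and from Day 3 "the study drug will be self-administered twice daily for the remaining 19 days of Cycle 1". All Part 1 subjects follow this schedule, as do the Part 2 subjects with PK assessment (at least 12).

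Section 7.2.2 (Replacement) attaches a consequence: "subjects who took less than 80% of the required study drug (BAY 1163877) in Cycle 1 (see Section 8.7) will be replaced", with the aim of having 3 evaluable subjects per cohort. Section 10.2 (Analysis sets) separately defines who enters the MTD evaluation: subjects who completed Cycle 1, or who stopped during it because of an adverse event or DLT.

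**The concern.** The parenthesis offers doses and days as interchangeable ways of stating one threshold. They are interchangeable only if every counted day carries two doses, and on the PK schedule Day 1 carries one. Section 8.7 also has the first administration take place with a member of the site team, so for a subject who starts on Day 1 that day is normally a documented dosing day.

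A subject at the boundary could therefore be compliant by days and non-compliant by doses. Section 7.2.2 sends the reader to Section 8.7 for this decision, so two sites could treat the same record differently: one replaces the subject, the other does not. Every dose-escalation subject is on this schedule.

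**Working it through.** **Inputs**
- Required share: 80% of planned medication (Section 8.7).
- Doses in Cycle 1 with PK assessment: 1 on Day 1, 0 on Day 2, 2 on each of the 19 days from Day 3 to Day 21 (Sections 6 and 8.4.2.1).
- Doses in a cycle without the PK schedule: 2 on each of 21 days.

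**Reproducing the plan's figures**
- Planned doses with PK: 1 + 0 + 19 × 2 = 39. Limit: 0.80 × 39 = 31.2, rounded up to 32 (32/39 = 82.1%). This agrees with the stated 32.
- Dosing days with PK: 1 + 19 = 20. Limit: 0.80 × 20 = 16. This agrees with the stated 16.
- Without PK: 0.80 × 42 = 33.6, rounded up to 34; 0.80 × 21 = 16.8, rounded up to 17. Both agree with the stated figures.

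Each number is reproduced separately. The remaining question is whether the two members of each pair mean the same thing.

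**Are the pairs equivalent?** Assume both doses are taken on every counted twice-daily day.
- Without PK: 17 × 2 = 34 doses (34/42 = 81.0%). Equivalent.
- With PK, Day 1 counted: the total for d dosing days is 1 + 2(d − 1).

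| Dosing days incl. Day 1 | Doses | Share of 39 | Day limit (16) | Dose limit (32) |
|---|---|---|---|---|
| 15 | 29 | 74.4% | fails | fails |
| 16 | 31 | 79.5% | meets | fails |
| 17 | 33 | 84.6% | meets | meets |

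- With PK, Day 1 not counted: 16 × 2 = 32 doses (82.1%), or 33 with the Day 1 dose added. Both limits are met.

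The limits separate in one row only: Day 1 plus 15 complete twice-daily days, with four of the 19 twice-daily days missed entirely.

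**The case against.** The strongest reply is that the parenthesis explains itself. In both pairs the days are half the doses (32/16 and 34/17), so the days can be read as the dose count restated in full twice-daily days. On that reading Day 1 is not one of the 16 and the limits agree. This is a fair reading, but the text does not state it, and 16 is also exactly 80% of the 20 dosing days, Day 1 included. Neither reading is forced.

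A second reply is that the operative rule is the share of drug. Sections 8.7 and 7.2.2 both speak of 80% of the medication, and 31 of 39 is below that whatever the parenthesis says. Doses are also what the diary records. This stands as a reason to let the dose count govern. It does not make the day alternative correct, because Section 8.7 is where Section 7.2.2 sends the reader.

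Two stronger inferences are tempting, and the document does not support either:
- **That the mismatch alters the DLT denominator, where one subject is a third of a cohort of 3.** Section 10.2 sets no compliance criterion. A subject with 31 doses who completed Cycle 1 is in the MTD evaluation under either limit. What changes is whether a further subject is enrolled.
- **That 16 days could mean as few as 16 doses (16/39 = 41.0%), one on each day.** The same parenthesis equates 16 days with 32 doses and with 80%, so this reading contradicts the sentence it comes from.

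**Conclusion.** The point holds as a small inconsistency in a decision threshold. The dose limit of 32 is correct. The day limit of 16 is not its equivalent if Day 1 is counted, because it then admits a subject at 31 of 39 doses (79.5%).

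The gap is one dose, and with fully dosed days it changes the classification of subjects with exactly 31 doses only. The consequence is confined to replacement under Section 7.2.2. The pair for cycles without the PK schedule is consistent for fully dosed days.

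The conclusion assumes that Day 1 counts as a dosing day and that counted days are fully dosed; Section 8.7 defines neither. It also leaves out the Day -3 single dose of the tablet bridging and food-effect subjects, since Section 8.7 does not say whether that dose counts toward Cycle 1 compliance. If it did, 40 doses would be planned, and 16 days including both single-dose days would hold at most 2 + 14 × 2 = 30 doses (75%). The 32-dose limit would still be exactly 80% of 40.

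**What to change.** In Section 8.7, delete the 16-day alternative for Cycle 1 with PK assessment and state the limit in doses only: at least 32 of the 39 planned doses. Section 7.2.2 can keep its cross-reference unchanged.

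The 34-dose / 17-day pair need not change, although giving it in doses only (34 of 42) would make the sentence uniform.

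The cost is one deleted phrase. The diary already records the date, time and amount of each intake, so no new data are needed.
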